SAP Version	Approval Date Protocol Version (Date) on which SAP is Based		Change	Rationale
1.0	8 Apr 2022	Amendment 01	Not Applicable	Original version
2.0	15 Jun 2022	Amendment 01	Section 4.3.1.2: Added calculation of annualized rate for retrospective period. Clarified definition of total duration of OCS administration. Added derivation method of eosinophil count. Section 6.2.2 or Section6.2.4: Corrected the ambiguous wording of "first dose of Nucala". Section 6.2.2: Added the definition of observation period for missing case.	Clarifications and additional considerations were required for valid analyses.
3.0	12 Dec 2022	Amendment 01	Added summaries for: - ANCA+/- - EGPA remission - Immuno-suppressive therapy - Asthma exacerbation - Average daily dose of OCS - Annualized rate of hospitalization for EGPA- related events - Annualized rate of ER/unscheduled visit for EGPA-related events	Clarifications and additional considerations were required for valid analyses.
4.0	18 Apr 2023	Amendment 01	"Active + worsening" category was added for the summaries of clinical	Clarifications and additional considerations

SAP Version	Approval Date	Protocol Version (Date) on which SAP is Based	Change	Rationale
			symptoms as assessed by 9 organ-systems Analysis of Annualized Rate (event/year) of Asthma Exacerbation for each of the 3 categories is added The definition of follow-up is changed The definition and the assessment point of EGPA relapse is changed A line plot is added for OCS	were required for valid analyses.
5.0	17 May 2023	Amendment 01	The duration between the start of retrospective period to the end of observation period summary were added The definition of the observation period and the follow-up period is changed	They are considered imperative to evaluate the safety of Nucala. The definition is aligned with the standard exposure definition of

1. INTRODUCTION

The purpose of this SAP is to describe the planned analyses to be included in the Clinical Study Report for Study 213684.

This SAP will be provided to the study team members to convey the content of the Statistical Analysis Complete (SAC) deliverable.

If a post-hoc analysis is required after the planned analysis has been performed, a separate analysis specification will be prepared for that purpose.

1.1. Objectives and Endpoints

Objectives	Endpoints
Primary	
• To investigate the long-term safety of Nucala in adult patients with EGPA	• Frequency of Adverse events (AEs)/ serious adverse events (SAEs)
	• Frequency of AEs related to Nucala (adverse drug reactions, ADRs)
	• Frequency of AEs of special interests (AESI)
Secondary	
• To investigate the long-term effectiveness of Nucala in adult patients with EGPA	• Proportion of participants with clinical symptoms as assessed by 9 organ-systems (i.e. systemic, skin, mucous membranes/eyes, ears/nose/throat, chest, cardiovascular, abdominal, renal, nervous system)
	• Proportion of participants with EGPA relapse ^a
	• Annualized rate (event/year) of hospitalization for EGPA-related events
	• Annualized rate (event/year) of emergency room/unscheduled visit for EGPA-related events
	• Average daily dose (prednisolone- equivalent) of oral corticosteroid (OCS) over 96 weeks
	• Proportion of participants in the dosing categories [*] relative to average

Objectives	Endpoints
	daily OCS (prednisolone-equivalent) over 96 weeks * 0 mg/day 0 mg/day < < 4 0
	$mg/day, 4.0 mg/day < \leq 7.5 mg/day,$ 7.5 mg/day <
Exploratory	
CCI	

a. EGPA relapse is defined as any of the following with worsening EGPA. 1) Increased dose of OCS. 2) Initiation/increased dose of immuno-suppressive agents. 3) EGPA treatment with hospitalization.
b. EGPA recurrence is judged by investigator based on the following definitions (only in participants who have been withdrawn from/terminated the Nucala treatment and entered the follow-up period due to symptom improvement per clinical judgement):1) Initiation/increased dose of OCS, 2) Initiation/increased dose of immuno-suppressive agents, 3) Hospitalization in association with the EGPA treatment.

1.2. Study Design

Overview of Study Design and Key Features											
Retrospective Data (before the first dose of	:	B	aseline I								
Nucala for EGPA)	Nucala for EGPA)						_				
Minimum	of 96 weeks of	Screeni	ng		Nucala	300mg	SC (120) partic	ipants)		
Nucala	Wook ~-/	1	0	12	24	36	48	60	72	86	96
	WEEK -	•	ų 	12	At any t	ime, decision	40			80	
					to discor for a	ntinue Nucala ny reason	Foll	low-up	Period		•
Design	This is a	single	e-arm,	multi-	center,	prospec	tive, no	on-inte	rventio	nal,	
Features	observati	ional s	study to	o asses	s the lo	ong-tern	1(2 to	4 years	s) real-	world	
	safety an	d effe	ctiven d Nuc	ess of l ala tre	Nucala atment	in adult	: patien veeks (its with	EGPA	who have a w	ave
	after its r	narke	t launc	h in Ja	ipan an	d who c	omplet	ted the	Nucala	PMS	.5)
	study (sp	oecial	drug u	se inve	estigatio	on; Prot	ocol No	o. 2085	505,		
	NCT035	57060)). To r	eflect	the real	l-world	setting	, inclus	sion and	d limited	ta
	the mini	mum 1	ria as v equire	d. Apr	roxima	ntant u ntely 120) partic	cipants	ria are will be	e enrolle	to ed
	in the study.										
	The primary objective is to investigate the long-term safety of Nucala,										
	with special attention to AEs, AESI, and SAEs, in adult patients with										
	EGPA in Japan. The effectiveness of Nucala will also be investigated as secondary and exploratory objectives. Endpoints for effectiveness are										
	included in reference to endpoints in the PMS study.										
Study	This study is an observational study that does not involve the										
interventio	administration of study treatment intervention. According to the Japanese										
n	prescribing information for Nucala, 300 mg mepolizumab is injected subcutaneously every 4 weeks in adult patients with ECPA, who										
	inadequa	telv r	espond	to oth	er exis	ting the	rapies.	Partici	pants r	eceive	
	marketec	l prod	ucts of	Nucal	la in an	y of the	approv	ved for	mulatio	ons;	
	lyophilized products and/or liquid products (prefilled syringe/auto-										
	injector pen).										
	This study is composed of three periods: screening period, observation period and follow-up period.										
	Screenin	ıg per	iod:								
	During th	he scr	eening	period	l (0-4 w	veeks), a	all parti	icipant	s are as	sessed	to
	determin	e whe	ther th	ey me	et the e	ligibility	y criter	1a. Reti	rospect	ive data	ı nd
	laborator	y para	ameter	s befor	e the fi	rst dose	of Nu	cala (at	t least 9	96 week	IU S
	[approxi	mately	y 2 yea	rs] bef	fore). T	hese ret	rospect	tive dat	ta shou	ld be fr	om

	physician source/medication record. By using the retrospective data, information could be provided about the change from pre-Nucala exposure to the end of this study, of which a period would be approximately 4 years.
	Any participant who completes assessments during the screening period but does not continue in the study beyond Baseline or is subsequently found to be ineligible for the study prior to Baseline, is classified as Screen Failure. Information collected for the participant classified as Screen Failure is detailed in the guideline for eCRF entry. Re-screening is permitted once only.
	Observation period:
	During the observation period, which is scheduled for 96 weeks (approximately 2 years) at maximum, safety and effectiveness data are obtained at approximately 12-week intervals. The intervals may be shorter/longer or may be irregular depending on the usual pattern of healthcare visits.
	Any data collected during the observation period are entered into eCRF. The assessments in the routine clinical practice during the observation period are shown in the protocol Section 9.1 (Appendix 1).
	Follow-up period:
	The follow-up period is only applicable to participants who have discontinued the treatment of Nucala due to any reason. The assessments in the routine clinical practice during the follow-up period are shown in the protocol Section 9.1 (Appendix 1).
	In case EGPA symptoms are deteriorated in a participant who previously discontinued the treatment of Nucala due to improvement of EGPA symptoms, the participant can receive the re-treatment of Nucala during the follow-up period. The participant who received the re-treatment of Nucala continues the assessments in the follow-up period.
Study interventio n Assignment	Not Applicable
Interim Analysis	The purpose of the interim analysis that for present results of the analysis for the primary outcome of the long-term safety of Nucala, and the secondary outcomes of the long-term effectiveness of Nucala using dataset including data until 48 weeks post-exposure. This analysis does not lead to a decision to amend the design or to stop the study.
	The interim analysis is carried out using interim dataset.
	All required database cleaning activities in accordance with the Data Management Plan (DMP) have been completed and interim database lock (DBL) has been declared by Data Management.

	Also, the interim analysis is performed for presentation at academic conference using dataset including data until 48 weeks post-exposure The Clinical Study Report is created at the interim analyses.				
Final Analysis	 The final planned analyses will be performed after the completion of the following sequential steps: 1. All participants have completed the study or been withdrawn as defined in the protocol. 2. All required database cleaning activities have been completed and final DBL has been declared by Data Management. The Clinical Study Report will be created at the final analyses. 				

2. STATISTICAL HYPOTHESES

This is a descriptive study. The study is not powered to detect differences and no formal statistical hypothesis testing will be performed for any of the endpoints.

3. ANALYSIS SETS

Analysis Set	Definition / Criteria	Analyses Evaluated		
Screened Population	• All participants who signed the ICF and who completed the screening.	Study PopulationScreening		
	1 0	Failure		
All Subjects Enrolled (ASE)	• All participants enrolled into the study meeting the eligibility criteria for the study.	Study Population		
Treated Population (TP)	• All participants in the ASE Population who have received at least 1 injection of Nucala.	Study PopulationSafetyEfficacy		

The populations for analyses are defined as below.

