#### **Screening period**

During the screening period (0-4 weeks), all participants are assessed to determine whether they meet the eligibility criteria. Retrospective data are collected for reference regarding the clinical symptoms/findings and laboratory parameters before the first dose of Nucala (at least 96 weeks [approximately 2 years] before). These retrospective data should be from physician source/medication record. By using the retrospective data,

information could be provided about the change from pre-Nucala exposure to the end of this study, of which a period would be approximately 4 years.

Any participant who completes assessments during the screening period but does not continue in the study beyond Baseline or is subsequently found to be ineligible for the study prior to Baseline, is classified as Screen Failure. Information collected for the participant classified as Screen Failure is detailed in the guideline for eCRF entry. Rescreening is permitted once only.

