# 4.1. Analysis Populations

The populations for analyses are defined as shown below.

Population	Definition / Criteria	Analyses Evaluated
All Subjects Enrolled (ASE)	All participants     enrolled into the study     meeting the eligibility     criteria for the study.	Study Population
Treated Population (TP)	All participants in the ASE study population who have received at least 1 injection of	

Study Population

Safety

Efficacy

Population	Definition / Criteria	Analyses Evaluated
	Nucala.	

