# 4.3. Summary of Patient Characteristics

Characteristics of enrolled participants collected at baseline will be described. This will include demographic information as well as disease characteristics. Results will be used to describe ASE population. This analysis is planned to be performed prior to and/or at the last participant first visit, depending on recruitment, and will not require formal statistical analysis. This analysis will not lead to a decision to amend the design or stop the study, and will be described further in the RAP.

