4. STATISTICAL ANALYSES

4.1. General Considerations

4.1.1. General Methodology

The study population analyses will be based on the All Subjects Enrolled (ASE) population, unless otherwise specified. The Treated Population (TP) will be used for all safety and efficacy analyses.

Confidence intervals will use 95% confidence levels unless otherwise specified.

Unless otherwise specified, continuous data will be summarized using descriptive statistics: n, mean, standard deviation (SD), median, minimum and maximum. Categorical data will be summarized as the number and percentage of participants in each category.

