4.2.2. Main analytical approach

The primary analyses will be based on the TP. Adverse events (AEs) will be coded using the Medical Dictionary for Regulatory Activities (MedDRA), with the maximum intensity of each AE determined by the investigator (as mild, moderate, severe or unknown).

All AEs, ADRs, SAEs, AEs leading to withdrawal from study, and AESIs will be summarized by the observation period and the total period (the observation period and the follow-up period), respectively. A separate summary of AEs by maximum intensity will be produced by the observation period and the total period, respectively.

The frequency and percentage of all AEs will be summarized and displayed in two ways: 1) in descending order by PT only and 2) in descending order by SOC and PT.

Separate summaries will be provided for ADRs. An ADR is defined as an AE for which the investigator classifies the possible relationship to study intervention as "Yes". A worst-case scenario approach will be taken to handle missing relatedness data, i.e. the summary table will include events with the relationship to study intervention as 'Yes' or missing. The summary table will be displayed by SOC and PT. The relationship of primary SOCs, Preferred Terms, and verbatim texts will be listed.

The number and percentage of participants who experienced the serious adverse event will be summarized.

The following will be considered adverse events of special interest (AESI) for the purpose of analyses: Hypersensitivity (including anaphylaxis), infections and malignant tumors, defined as safety specifications in the Japanese RMP.

AESI	Definition	Dictionary code
Hypersensitivity (including anaphylaxis)	Anaphylaxis reaction (SMQ/narrow)	20000021 (narrow)
	Excluding "10078117: Eosinophilic granulomatosis with polyangiitis" from PT contained in Hypersensitivity (SMQ/narrow)	20000214 (narrow)
Infections	Infections: Infections and infestations(MedDRA/J SOC)	MedDRA/J SOC: 10021881
Malignant tumors	Malignant tumors (SMQ/narrow)	20000227 (narrow) 20000228 (narrow)
	Lymphoma malignum (SMQ/narrow)	20000215 (narrow)

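### ASE, and the safety set TP nested in it, is worded to require meeting the eligibility criteria; taken literally this drops treated participants found ineligible late, against the plan's apparent intent

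*SAP*

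**What the plan says.** SAP 3 defines ASE as "All participants enrolled into the study meeting the eligibility criteria for the study", and Protocol 4.1 has the same condition. TP is nested in ASE: the SAP has "All participants in the ASE Population who have received at least 1 injection of Nucala", and the protocol matches it with "All participants in the ASE study population who have received at least 1 injection of" Nucala.

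TP is the only safety set. SAP 4.1.1 states "The Treated Population (TP) will be used for all safety and efficacy analyses", and SAP 4.2.2 states "The primary analyses will be based on the TP". No sensitivity analysis is planned for the primary endpoint (SAP 4.2.3).

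On ineligibility, the Screening period text in Protocol 3.1 covers discovery before Baseline: a participant "subsequently found to be ineligible for the study prior to Baseline, is classified as Screen Failure". SAP 1.2 repeats this. Neither document states what happens to a participant who is enrolled, treated and only later found to breach a criterion.

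On deviations, Protocol 4.2 counts inclusion/exclusion deviations among the important ones, and SAP 6.1.3 summarises important deviations on the ASE. SAP 6.1.3 also plans a separate listing of inclusion/exclusion deviations, without naming a population. There is no per-protocol set.

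**The concern.** Long-term safety is the primary objective, and the study is sized to see a single case of an uncommon event. A safety set should contain everyone treated and observed. As worded, the definition makes membership depend on eligibility, with no limit on when a breach is discovered.

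Late discovery is plausible. The Schedule of Activities lets Screening and Week 0 fall on the same day, and some criteria rest on past records, such as an earlier interruption of treatment. Deviations are reviewed shortly before database freeze or lock, when the events have already been recorded. Under the literal wording, that review could remove a participant and their events from the AE, SAE, ADR and AESI tables. It could also make the final TP omit someone who was counted in the 48-week interim TP. Two programmers could build different sets from the same text.

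The loss would be limited to analyses on TP. Events are still collected from consent (Protocol 6.2.1), and the final report includes a summary of events related to the sponsor's products that is not tied to TP (Protocol 9.6). Unrelated events have no such fallback.

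**Working it through.** **1. Literal reading against the deviation plan**

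- ASE contains only enrolled participants who meet the criteria (SAP 3, Protocol 4.1).
- Eligibility deviations are important deviations (Protocol 4.2), and important deviations are summarised on the ASE (SAP 6.1.3).
- If both are taken literally, the eligibility rows of that summary must be empty, so the two instructions conflict. The separate inclusion/exclusion listing names no population and need not be empty.

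**2. Evidence on intent**

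- Protocol 3.1 and SAP 1.2 place the eligibility assessment in the screening period.
- SAP 3 has a Screened Population row that handles screening failures. In that sequence, the eligibility phrase in the ASE row most naturally separates enrolled participants from screening failures.
- Protocol 4.3 says "Characteristics of enrolled participants collected at baseline will be described" and then "Results will be used to describe ASE population", treating enrolled participants and ASE as the same group.
- Eligibility-deviation outputs are planned, and no per-protocol set exists.

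All of this points to keeping participants found ineligible late, but no sentence says so.

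**3. The plan's own sample-size figures** (Protocol 3.5, SAP 5)

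Inputs: event frequency 1.5%; target probabilities 80%, 70% and 90%; dropout 10%. The formula is P(at least one case) = 1 − 0.985^n.

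- n = 107 gives 80.15% and n = 106 gives 79.85%, so 107 is reproduced.
- n = 80 gives 70.15% and n = 153 gives 90.10%, so both are reproduced.
- 107 / (1 − 0.10) = 118.9, rounded up to 119, in line with approximately 120.

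**4. Effect of excluding k participants from a TP of 120**

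The documents do not give k; 0 to 6 (0 to 5%) is an assumption.

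| k | n in TP | P(at least one case of a 1.5% event) |
|---|---|---|
| 0 | 120 | 83.7% |
| 3 | 117 | 82.9% |
| 6 | 114 | 82.1% |

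The fall at k = 6 is 83.7 − 82.1 = 1.6 percentage points. Without a dropout deduction, the probability first drops below 80% at the 14th exclusion (120 − 14 = 106).

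If the planned 10% dropout is also deducted (rounding down), n is 108, 105 and 102, and the probabilities are 80.5%, 79.5% and 78.6%. This is a pessimistic bound, because treated participants who drop out remain in TP.

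**5. Effect on a single-case row**

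If the omitted participants carry average risk, a given single-case row is lost with probability k/120: 0.8% for k = 1, 2.5% for k = 3 and 5.0% for k = 6.

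**The case against.** The strongest objection is that the documents already settle the matter. Eligibility is assessed during screening, the Screened Population row deals with screening failures, and the deviation summary on ASE makes sense only if eligibility deviators belong to ASE. The study is descriptive, the criteria are kept to a minimum, and the number affected may be zero.

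Most of this stands. It makes the inclusive reading the likelier intent and keeps the severity low. It does not remove the defect, because the definition that a programmer will implement carries an unqualified eligibility condition, and the inclusive reading has to be inferred from other sections.

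A reader might also infer from SAP 6.1.1 that a participant found ineligible late could be labelled a screening failure, since that section refers to not meeting the criteria at Screening and omits when the breach was found. The documents do not support this: SAP 1.2 limits the label for ineligibility to what is found before Baseline, and the two sections can be read together without conflict. A short clarification there is still worthwhile.

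**Conclusion.** The wording error is real and of low severity. Followed as written, the ASE definition removes treated participants found ineligible after Baseline from the primary safety tables and conflicts with the planned deviation summary. The expected effect is small: with 0 to 6 of 120 excluded, the detection probability for a 1.5% event stays between 83.7% and 82.1%. That range rests on an assumed number of exclusions, on a TP of 120 before them, and on treated dropouts staying in TP.

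Two stronger conclusions are not supported. One is that the sponsor intends to exclude late-found ineligible participants from safety; the surrounding sections suggest the opposite. The other is that the sample size is undermined; the stated 107 and approximately 120 reproduce and do not depend on this point. What remains is that one omitted participant could turn a single-case row into zero.

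**What to change.** - **SAP 3 now, Protocol 4.1 at the next amendment.** Define ASE as every enrolled participant except Screen Failures (ineligibility found before Baseline). Add that eligibility deviations identified at or after Baseline are reported but do not remove a participant from ASE or TP. Keep TP as ASE participants with one or more Nucala injections.
- **SAP 6.1.3.** Run both the important-deviation summary and the inclusion/exclusion listing on this ASE.
- **SAP 6.1.1.** Add to the screening-failure definition only that the ineligibility was found before Baseline. State that nobody dosed at or after Week 0 in this study is a screening failure. Do not import the Protocol 3.1 clause about not continuing past Baseline: it could label a participant dosed at Week 0 a screening failure while the new ASE text keeps that participant in TP.

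The cost is a few definition lines and no new data. The downside is that a few participants outside the target population enter the effectiveness summaries; the listing identifies them.

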4. STATISTICAL ANALYSES

4.1. General Considerations

4.1.1. General Methodology

The study population analyses will be based on the All Subjects Enrolled (ASE) population, unless otherwise specified. The Treated Population (TP) will be used for all safety and efficacy analyses.

Confidence intervals will use 95% confidence levels unless otherwise specified.

Unless otherwise specified, continuous data will be summarized using descriptive statistics: n, mean, standard deviation (SD), median, minimum and maximum. Categorical data will be summarized as the number and percentage of participants in each category.

